Research Program

(Version number: 02 Version date: 2022-05-03)

Project name: Clinical efficacy and safety of real-world patients with refractory rheumatoid arthritis (D2TRA) treated with Abciap in combination with Janus kinase (JAK) inhibitors

Bidder: Zhejiang Provincial People's Hospital

Department: Rheumatology and Immunology

Principal Investigator: [name]

Investigator's statement and protocol signature page

As the principal person in charge of this research project, I will follow the Ethical Review of Biomedical Research Involving Human Beings (2016) of the Ministry of Health, the Declaration of Helsinki (2013) of the WMA and the International Ethical Guidelines for Human Biomedical Research (2002) of the CIOMS and the ethical principles of the GCP, using the protocol approved by the ethics committee under the guidance of the quality management specifications for drug clinical trials, and conducting the study in accordance with the requirements of this protocol to ensure the scientific validity of the study and to protect the health and rights of the subjects.

Name: _____

Signature: _____

Date: _____

Program Summary

Program Title	Clinical efficacy and safety of real-world patients with refractory rheumatoid arthritis (D2TRA) treated with abciap in combination with Janus kinase (JAK) inhibitors
Version number/version date	02/ 2022-05-03
Sponsors and Participating Units	Zhejiang Provincial People's Hospital
Principal Investigator	
Nature of Research	Clinical Studies
Purpose of the study	To observe the clinical efficacy and safety of Abciap combined with JAK inhibitor in the treatment of D2TRA patients
Sample size	90
Research Subjects	Patients with refractory rheumatoid arthritis

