Research Methodology	Real-world observational study. Prospectively, 90 patients with D2TRA who were ineffective to conventional disease-modifying antirheumatic drugs and ineffective to treatment with 2 or more biological/targeted disease-modifying antirheumatic drugs and treated with abciap combined with JAK inhibitors attending the outpatient and inpatient departments of Zhejiang Provincial People's Hospital from March 2022 to March 2024 were included as an observational group. Thirty patients with D2TRA treated with abciap alone in the outpatient and inpatient departments of Zhejiang Provincial People's Hospital from August 2020 to November 2021 were selected as the historical control group. There was no statistically significant difference between the observation group and the control group in terms of gender, age, disease duration, number of pressure pain in 28 joints, number of swelling in 28 joints, and DAS28 score ($P > 0.05$). The drugs were billed according to the maximum number of days of medical insurance (4 weeks), and the changes in laboratory tests, number of pressure pain in 28 joints, number of swelling in 28 joints, and DAS28 score were observed in the group treated with Abacap

	
combined with JAK inhibitor, and the before-and-after self comparison was performed at 0, 4, 8, 12, 16, 20, and 24 weeks, along with the changes in joint ultrasound and adverse effects. Also observe the changes in laboratory tests, number of pressure pain in 28 joints, number of swelling in 28 joints, and DAS28 score in the group treated with Abacap alone, and perform a before-and-after self-comparison at 0, 4, 8, 12, 16, 20, and 24 weeks, as well as observe the changes in joint ultrasound and adverse reactions. In addition, we observed the changes in laboratory tests, the number of pressure pain in 28 joints, the number of swelling in 28 joints, and the DAS28 score between the patients in the Abacap combined with JAK inhibitor treatment group and the Abacap treatment group alone at 0, 4, 8, 12, 16, 20, and 24 weeks, and compared them between the two groups for a statistically significant difference at $P < 0.05$. We also observed the changes in joint ultrasound and adverse effects between the two groups. Changes in adverse reactions

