(3) Specific study: 90 D2TRA patients who were ineffective to conventional disease-modifying antirheumatic drugs and ineffective to treatment with 2 or more biological/targeted disease-modifying antirheumatic drugs and treated with Abacap combined with JAK inhibitors attending the outpatient and inpatient departments of Zhejiang Provincial People's Hospital from March 2022 to March 2024 were prospectively included as the observation group. Thirty patients with D2TRA treated with abciap alone in the outpatient and inpatient departments of Zhejiang Provincial People's Hospital from August 2020 to November 2021 were selected as the historical control group. There was no statistically significant difference between the observation group and the control group in terms of gender, age, disease duration, number of pressure pain in 28 joints, number of swelling in 28 joints, and DAS28 score ($P > 0.05$). Drugs were billed according to the maximum number of days of medical insurance (4 weeks), and changes in laboratory tests, number of pressure pains in 28 joints, number of swelling in 28 joints, and DAS28 score were observed in the Abciap combined with JAK inhibitor treatment group, and pre- and post-self comparisons were performed at 0, 4, 8, 12, 16, 20, and 24 weeks, along with changes in joint ultrasound and adverse effects. The changes in laboratory tests, number of pressure pains in 28 joints, number of swelling in 28 joints, and DAS28 scores were also retrospectively collected from the group treated with Abacap alone, and before and after self-comparison was performed at 0, 4, 8, 12, 16, 20, and 24 weeks, along with observation of changes in joint ultrasound and adverse effects. In addition, we observed the changes in laboratory tests, the number of pressure pains in 28 joints, the number of swelling in 28 joints, and the DAS28 score at 0, 4, 8, 12, 16, 20, and 24 weeks in the group treated with Abatacept combined with JAK inhibitor and the group treated with Abatacept alone, and compared them between the two groups for a statistically significant difference at $P < 0.05$. We also observed the changes in joint ultrasound and The changes of adverse reactions were also observed between the 2 groups.

5. Research Methodology:

Enrollment criteria (diagnostic criteria, inclusion criteria, exclusion criteria)

(1) Diagnostic criteria

The diagnostic criteria for D2TRA refer to the definition criteria proposed by EULAR 2021:

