No intervention factors were imposed on the study subjects in the study. Prospectively, 90 patients with D2TRA who were ineffective to conventional disease-modifying antirheumatic drugs and ineffective to treatment with 2 or more biological/targeted disease-modifying antirheumatic drugs and treated with Abacap combined with JAK inhibitors attending the outpatient and inpatient departments of Zhejiang Provincial People's Hospital from March 2022 to March 2024 were included as the observation group. Thirty patients with D2TRA treated with abciap alone in the outpatient and inpatient departments of Zhejiang Provincial People's Hospital from August 2020 to November 2021 were selected as the historical control group. There was no statistically significant difference between the observation group and the control group in terms of gender, age, disease duration, number of pressure pain in 28 joints, number of swelling in 28 joints, and DAS28 score ($P > 0.05$). The dosage was 125 mg per dose by subcutaneous injection once a week, and the dosage was 5 mg per dose by oral injection twice a day. The drug was billed according to the maximum number of days of medical insurance (4 weeks), and patients were observed for rheumatoid factor, anti-cyclic citrullinated peptide antibodies, immunoglobulins (IgG, IgA and IgM), C-reactive protein, blood sedimentation, white blood cells, platelets, ghrelin, glutamic aminotransferase, glutamic oxalacetic aminotransferase, globulin, creatinine, glomerular filtration rate, 28 joints at 4, 8, 12, 16, 20 and 24 weeks before and after drug administration number of pressure pain, number of swelling in 28 joints, joint ultrasound, change in DAS28-ESR score and adverse effects. To observe the changes in laboratory test indices, number of pressure pain in 28 joints, number of swelling in 28 joints, and DAS28 scores in the Abciap combined with JAK inhibitor treatment group, before and after self-comparison at 0, 4, 8, 12, 16, 20, and 24 weeks, as well as the changes in joint ultrasound and adverse effects. Also retrospectively collected the changes in laboratory test indices, number of pressure pain in 28 joints, number of swelling in 28 joints, and DAS28 score in the group treated with Abacap alone, and performed a before-and-after self-comparison at 0, 4, 8, 12, 16, 20, and 24 weeks, while observing the changes in joint ultrasound and adverse effects. In addition, we observed the changes in laboratory indices, the number of pressure pain in 28 joints, the number of swelling in 28 joints, and the DAS28 score between the Abciap and JAK inhibitor treatment groups at 0, 4, 8, 12, 16, 20, and 24 weeks, and compared them between the two groups. The changes in joint ultrasound and adverse effects between the two groups were also observed, so as to observe the clinical efficacy and safety of the Abciap combined with JAK inhibitor treatment group. $DAS28 \leq 2.6$ was defined as clinical remission, $2.6 < DAS28 \leq 3.2$ as low activity, $3.2 < DAS28 \leq 5.1$ as moderate activity, and $DAS28 > 5.1$ as high activity.

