including the Declaration of Helsinki ethical guidelines for human medical research and the relevant Chinese clinical research study norms and regulations. In the course of the study, if there is a need to revise this protocol, the revised protocol must be submitted to the Ethics Committee again for approval before implementation.

The Informed Consent Form for this study has been approved by the Medical Ethics Committee. If the Informed Consent Form is amended in writing, it will be sent to the Ethics Committee for approval to obtain the subject's consent again. Before the start of the study, the investigator provides patients with detailed information about the study, including the nature of the study, the purpose of the study, the possible benefits and risks, and the rights and obligations of the patients. The patient is fully informed and agrees, and signs the Informed Consent Form before the study can begin.

11. Statistical analysis plan

SPSS software was used for statistical analysis. Normality tests were performed using the Kolmogorov-Smirnov test, and measures conforming to a normal distribution were expressed as mean \pm standard deviation ($\bar{x} \pm s$), and comparisons between groups were made using the two independent samples t-test; measures not conforming to a normal distribution were described by median and interquartile spacing, i.e., median (25th percentile, 75th percentile) [M(P25,P75)], and comparisons between groups were made using the Mann-Whitney U anecdotal test Comparisons between groups were made using the Mann-Whitney U anecdotal sum test; count data were expressed as percentages, and comparisons between groups were analyzed using the chi-square test or Fisher's exact probability method, with differences considered statistically significant at $P < 0.05$.

12、 Form of publication of research results

Published 1-2 papers

13.Data Logging Form

Observed indicators		Week 0	Week 4	Week 8	Week 12	Week 16	Week 20	Week 24
Rheumatoid factor	IU/ml							
Anti-cyclic citrulli	U/ml							

nated peptide antibody								
Immunoglobulin G	g/L							
Immunoglobulin A	g/L							
Immunoglobulin M	g/L							
C-reactive protein	mg/L							
Blood sedimentation	mm/h							
Leukocytes	$\times 10^9/L$							
Blood platelets	$\times 10^9/L$							
Glutathione aminotransferase	U/L							
Glutathione transa	U/L							

minase								
Globulin	g/L							
Creatinine	umol/L							
Glomerular filtration rate	ml/min							

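### Baseline comparability with 30 historical controls rests on P > 0.05, which cannot show balance at 90 versus 30, and Section 11 names only unadjusted tests for this non-randomised contrast

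*Protocol*

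**What the plan says.** Section 4(3) of the protocol takes 90 combination patients "from March 2022 to March 2024 were prospectively included as the observation group". The 30 controls received abatacept alone between August 2020 and November 2021, and their follow-up data "were also retrospectively collected from the group treated with Abacap alone". The two periods do not overlap, and Section 7 says that treatment was not imposed by the study.

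On comparability the protocol offers one statement: "There was no statistically significant difference between the observation group and the control group in terms of gender, age, disease duration", followed by tender and swollen joint counts and DAS28, with P > 0.05. It stands in Section 4(3) and again in the Program Summary and Section 7 ("There was no statistically significant difference between the observation group and the control group"). The title block gives "Version number: 02 Version date: 2022-05-03".

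Laboratory values, joint counts and DAS28 are then set side by side at each visit, and the protocol "compared them between the two groups for a statistically significant difference" at the 0.05 level. Section 7 lists "the DAS28 score between the Abciap and JAK inhibitor treatment groups at 0, 4, 8, 12, 16, 20, and 24 weeks". Section 11, which is headed as the statistical analysis plan, says "comparisons between groups were made using the two independent samples t-test" when data are normal, with Mann-Whitney otherwise and chi-square or Fisher for counts. The protocol mentions no regression, matching, weighting or standardised differences.

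**The concern.** The sentence has two possible readings, and it fails on both. As a result, it could not have been known: at the version date enrolment of the 90 had barely started. As a comparability criterion in translated prose, it uses the wrong tool. A non-significant test with 30 patients on one side says little about balance, and no selection or matching rule is given that could deliver the promised outcome.

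This is the only between-group contrast in the study, so it is the only one that could speak to the JAK inhibitor's added effect. A reader told that the groups do not differ is invited to take an unadjusted difference as that effect, while Section 11 offers nothing to deal with measured baseline differences.

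A smaller point adds to this. The text speaks of comparing changes but includes week 0, where no change exists, so it is unclear whether changes or visit values are compared. The before-and-after comparisons within each group are not affected.

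**Working it through.** The protocol gives no baseline means, SDs or individual P values, so there is no figure of its own to reproduce. The inputs taken from it are 90 and 30 patients, the 0.05 level (two-sided assumed), the version date and the enrolment window.

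**1. Largest difference that passes.** Standard error of a standardised difference = √(1/90 + 1/30) = 0.2108. t(0.975, 118 df) = 1.980. Limit = 1.980 × 0.2108 = **0.417 SD**.

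**2. How often a true imbalance is missed** (noncentral t, 118 df): 0.2 SD, 84.4%; 0.3 SD, 70.8%; 0.4 SD, 53.1%.

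**3. Can the statement be promised?** If the groups are truly equal and the six tests are independent, all six pass with probability 0.95⁶ = 0.735. Independence is an assumption: DAS28 is built partly from the joint counts. Positive correlation raises the figure only slightly.

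**4. What could be known at the version date.** 1 March to 3 May 2022 is 63 of the 761 days to 31 March 2024, or 8.3%. With even accrual (assumed), 0.083 × 90 ≈ 7.5 patients, say 8. At 8 versus 30 the limit is t(0.975, 36 df) × √(1/8 + 1/30) = 2.028 × 0.398 = 0.81 SD.

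**5. Effect on the estimate.** Let r be the correlation between baseline and week-24 DAS28 (assumed 0.3 to 0.7, equal SDs). The change-score and baseline-adjusted estimates differ by (1 − r) × the observed baseline difference. The standard error of the change comparison is 0.2108 × √(2(1 − r)). At the largest passing difference:

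| r | Gap (SD) | SE (SD) | Gap / SE |
|---|---|---|---|
| 0.3 | 0.29 | 0.249 | 1.17 |
| 0.5 | 0.21 | 0.211 | 0.99 |
| 0.7 | 0.13 | 0.163 | 0.77 |

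**6. Effect on type I error.** Simulation, 100,000 runs per cell, 90 versus 30, no treatment effect, true baseline DAS28 imbalance of 0.4 SD (assumed). In case (a) both groups regress towards a common mean; in case (b) the baseline difference is stable over time. The adjusted test uses baseline DAS28 only. Rejection rates for r = 0.3 / 0.5 / 0.7:

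| Case, test | All studies (%) | Studies with baseline P > 0.05 (%) |
|---|---|---|
| (a) change score | 19.8 / 15.7 / 11.2 | 7.4 / 6.9 / 6.2 |
| (a) adjusted | 4.9 / 5.0 / 5.1 | 5.0 / 5.1 / 5.1 |
| (b) change score | 4.9 / 4.9 / 5.0 | 4.7 / 4.7 / 4.9 |
| (b) adjusted | 27.5 / 18.8 / 12.3 | 28.1 / 19.2 / 12.4 |

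If raw week-24 values are compared instead, the rates given a passed baseline are 5.7 / 7.0 / 7.8% in (a) and 38.2 / 31.4 / 24.3% in (b). Neither the change score nor the adjusted test is right in both cases.

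**The case against.** The strongest reply concerns weight and remedy.

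- **Typical size.** A shift of about one standard error occurs only at the edge of passing. Averaged over studies that pass, the gap is 0.43 to 0.28 standard errors with no true imbalance and 0.71 to 0.46 with a true 0.4 SD, for r from 0.3 to 0.7. Type I error given a passed baseline is near nominal for the change score. This stands, and it is why the harm is described as mainly false assurance.
- **The remedy is not uniformly better.** In case (b) the adjusted test rejects in 12 to 28% of null studies while the change score holds 5%. This stands too. It argues for reporting both estimates and ranking neither, not for leaving one alone.
- **Unlisted factors.** The larger confounding risk lies outside the six variables, and the suggested covariates come from that list. True; no model on these data removes that risk, so the contrast needs a supportive label.
- **Translation.** The whole protocol is in the past tense, including future work, so the sentence is probably an intended condition. That may be so, but P > 0.05 is no better as a condition.
- **Left to a separate plan.** Section 11 names no paired test either, so it may not be exhaustive. However, it carries the heading of the analysis plan and names the between-group tests. The point is about what it states, and the comparability sentence is wrong whatever another document adds.
- **Control data.** A row on the logging form does not prove that every retrospective control has DAS28-ESR at each visit. Fair, but the planned comparison at those visits depends on the same data.

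**Conclusion.** The concern holds and should be fixed. The comparability sentence cannot be a result for 90 patients at the version date, and as a criterion it cannot show balance: it allows observed differences up to 0.42 SD and misses a true 0.3 SD imbalance in 71% of studies. Those two figures need only 90, 30 and the two-sided 0.05 level. The 74% chance of passing all six tests assumes independence, and the figure of 8 patients assumes even accrual.

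The consequence for the between-group result is moderate. With r between 0.3 and 0.7, the choice of adjustment moves the estimate by 0.8 to 1.2 standard errors at the edge of passing, and by less on average. Change-score type I error among studies that pass is about 5 to 7% under the assumed 0.4 SD imbalance. The main damage is that readers are told the groups are comparable when nothing in the plan establishes it. Calendar period, retrospective control data and unmeasured reasons for treatment choice remain whatever is done.

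**What to change.** 1. Delete the non-significance sentence in the Program Summary, Section 4(3) and Section 7. After enrolment, report standardised mean differences for the baseline variables.
2. In Section 11, state that the between-group comparison uses change from baseline. Add alongside it a baseline-adjusted comparison of DAS28-ESR with baseline DAS28-ESR, age, sex and disease duration as covariates. Report both and read any disagreement cautiously, because they rest on different assumptions (cases (b) and (a) above). Do not rank one as correct, and do not require both to be significant.
3. State that the between-group result is supportive, given the different calendar periods, retrospective control data and unmeasured reasons for treatment choice.

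The cost is wording in three places, two or three sentences in Section 11 and one model. The protocol already names the covariates for both groups, and DAS28-ESR is on the logging form at every visit, so no new variables are needed; its availability in the control records should be confirmed. The drawbacks are a little more analysis, a covariate list that must stay short with 30 controls, and two estimates that may disagree. Because agreement is not required, no power is lost to a joint-rejection rule.

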①Case collection form: includes basic information of enrolled patients, related diseases, disease duration, treatment, and test data of related indicators for individual data analysis.

②Summary table: includes the patient's disease and related index examination data for overall data analysis.

2. Assessing the overall data situation

①Evaluate the integrity of each data source: timely recording of patient-related data to ensure data integrity.

②Evaluate the accuracy and consistency of aggregated data: randomly check whether the extracted data are consistent with those in the database to ensure data accuracy.

3. Data cleaning and collation

①Check for errors and outliers in the data that clearly defy common sense, and when found, first check that the same patient metadata are the same, then check how this data was collected, and finally how to assess whether it is an outlier from a technical point of view, by using relevant statistical indicators and methods such as setting upper and lower limits to deal with outliers.

②For special numbers, first mark "missing value", there is a perfect data dictionary to query the actual situation of this field, if not need to promptly communicate to confirm such issues

4. Data Collation

①Uniform formatting and naming rules for data

②Recoding of certain information to meet subsequent analysis needs

5. Data Visualization

Histograms, line graphs, scatter plots or heat maps are used to visualize the data of patient-related indicators to show the data results and trends more clearly, so that the study results can be presented more clearly.

6. Data Analysis

Complete the data and perform statistical analysis on those that meet the criteria

1) Frequency of data security and monitoring reports submitted to the ethics committee

The research in this project is a low-risk study, so an annual review frequency is used. Also, the principal investigator holds regular study meetings and notifies the ethics committee if there are changes in the risk/benefit ratio of the study.

10. Respect for ethical principles and related regulations

The study was conducted in strict compliance with international and domestic standards and norms,

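### Prospective combination data and retrospectively collected control data are compared by separate tests at seven fixed weeks, with nothing that makes the visits like for like

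*Protocol*

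**What the plan says.** Protocol section 4(3) states that the combination patients "were prospectively included as the observation group", with enrolment from March 2022 to March 2024. The comparator is "Thirty patients with D2TRA treated with abciap alone" between August 2020 and November 2021, and for them "DAS28 scores were also retrospectively collected from the group treated with Abacap alone". Section 7 repeats that the control data are retrospective. The Program Summary does not mention it and says only "Also observe the changes in laboratory tests, number of pressure pain in 28 joints" and so on for the control group.

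The between-group comparison covers laboratory values, joint counts and "the DAS28 score at 0, 4, 8, 12, 16, 20, and 24 weeks in the group treated with Abatacept combined with JAK inhibitor" against abatacept alone. For continuous measures section 11 says "comparisons between groups were made using the two independent samples t-test", or Mann-Whitney if a normality test fails, at P < 0.05. It names no repeated-measures method and no adjustment for the week-0 value.

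On data quality, section 9 requires timely completion at the specified time points, asserts complete collection for each subject, and asks for the reason where a value is missing. Its data-analysis item reads "Complete the data and perform statistical analysis on those that meet the criteria". On ultrasound, section 7 says "The changes in joint ultrasound and adverse effects between the two groups were also observed".

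**The concern.** The two groups' values arise differently. For patients enrolled prospectively, the team can see to it that a joint count and an ESR are obtained at each planned week. For controls treated before enrolment opened, a value exists at a given week only if routine care produced one. The rules in section 9 cannot be enforced on care already given, and nothing says which control record counts as, for example, week 12.

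A two-sample test at one visit drops every patient without a value there. If the chance of having a control value was related to how the patient was doing, the control mean describes a selected subset, and a difference can appear between equally effective treatments. More frequent scoring of active patients flatters the combination. More complete records in patients who stayed well flatter abatacept alone. This contrast is the protocol's only comparison with another treatment.

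**Working it through.** The protocol gives no effect size, SD, power or missing-data rate, so there is no stated figure to reproduce. What follows is illustration under stated assumptions.

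**Inputs from the protocol:** 90 and 30 patients, seven visits, significance level 0.05 (two-sided assumed).

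**Step 1: precision, if recording is unrelated to disease activity.** The difference detectable with 80% power, in SD units, is (1.960 + 0.842) × √(1/90 + 1/n), where n is the number of controls measured at that visit.

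| Controls measured | √(1/90 + 1/n) | Detectable difference (SD) |
|---|---|---|
| 30 | 0.211 | 0.59 |
| 20 | 0.247 | 0.69 |
| 15 | 0.279 | 0.78 |

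There is no bias in this case, and simulated type I error stayed at 4.9% to 5.1%.

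**Step 2: when bias arises.** If a control with value Y is measured with probability π(Y), the mean of the measured controls differs from the true control mean by Cov(Y, π(Y)) / E[π(Y)]. This is zero when π is constant. Its sign follows whether worse or better patients are measured more often.

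**Step 3: single-visit simulation.** Assumptions: 20,000 runs, no true effect, all 90 combination values present, and odds of a control being measured multiplied by the stated ratio per SD of DAS28. Each cell gives the spurious difference favouring the combination and the rejection rate.

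| Controls measured | Ratio 1.5 | Ratio 2 | Ratio 3 |
|---|---|---|---|
| 80% | 0.08 SD, 6% | 0.13 SD, 8% | 0.19 SD, 12% |
| 60% | 0.16 SD, 9% | 0.25 SD, 15% | 0.35 SD, 27% |

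**Step 4: longitudinal simulation.** Assumptions: DAS28 falling from 5.2 to 3.4 in both groups; random intercept SD 0.8, slope SD 0.035 per week, residual SD 0.5; 95% of combination values present. Control recording depends on the last recorded DAS28, with one probability if it was above 3.2 and another otherwise. Differences are combination minus control at week 24, by t-test.

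| Recording probability (above 3.2 / otherwise) | Levels | Change from week 0 |
|---|---|---|
| 0.9 / 0.4 | -0.30, 16% | -0.13, 8% |
| 0.9 / 0.25 | -0.45, 27% | -0.19, 10% |
| 0.9 / 0.75 (mild) | about 6% rejection | not shown |
| 0.4 / 0.9 (reversed) | +0.29, 12% | not shown |

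The first row leaves about 20 of 30 controls measured and produces a gap of about 11 percentage points in low disease activity (DAS28 ≤ 3.2). The results vary with the assumed curve: a straight-line decline gave -0.26 and 13% on levels in that row.

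*Hand check of the first row.* The week-24 SD is √(0.8² + (24 × 0.035)² + 0.5²) = √1.596 = 1.26. The standard error is 1.26 × √(1/85.5 + 1/20) = 0.31. The shift is 0.30 / 0.31 ≈ 0.96 standard errors, so the rejection probability is about P(Z > 1.96 - 0.96) = 16%, as simulated. In SD units the first two rows are 0.30/1.26 = 0.24 and 0.45/1.26 = 0.36, close to the 60% row of step 3.

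**Step 5: does a repeated-measures model help?** When recording depended on the last recorded value, a mixed model on all values had bias near zero and 3% to 5% rejection (150 runs in each of two scenarios, so imprecise). That result is expected, because the missingness is then explained by data in the model. When recording depended on current, possibly unrecorded activity, bias of -0.12 to -0.22 remained, with 7% to 11% rejection. The model reduces the problem and does not remove it.

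**The case against.** The strongest reply is that the protocol never says control values are missing. It describes control self-comparisons at all seven weeks and asserts completeness. Drugs were billed in 4-week blocks, which could have brought controls in at these intervals however they were doing. The combination group is in routine care too, since no intervention was imposed. All of this stands. A reader might infer that only those controls who happened to be measured enter each test, but the text does not establish that. Equally, 4-week billing does not show that a joint count and an ESR were done at each dispensing.

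Three other tempting readings also go too far:

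- **The combination group is nearly complete.** Exclusion 4 removes combination patients who cannot adhere, or who have serious adverse reactions and do not finish the course. That side may itself be a completer subset.
- **The section 13 form serves one group only.** The form is not assigned to either group.
- **Ultrasound is unusable because it has no score.** The form's table is damaged in the text available, so a blank cell proves little. Ultrasound is described as observed, without an explicit significance test.

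The protocol speaks of changes in DAS28. If change scores are tested, the week-0 value enters by subtraction and the illustrated bias falls by more than half.

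It can also be said that windows and missing-data rules belong in a statistical analysis plan not shown here. That is fair for the detail. The unequal data sources and the per-visit tests, however, are fixed in sections 4, 7 and 11.

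**Conclusion.** The point holds in a limited form. The protocol commits itself to comparing prospective with retrospective values at seven fixed weeks, using tests that discard patients without a value at that visit and, on levels, ignore the week-0 value. No common window aligns the visits, and the section 9 safeguards cannot reach past care.

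Whether this produces bias is unknown. With recording unrelated to disease activity, the loss is precision only. With strong dependence (0.9/0.4 to 0.9/0.25), the spurious difference is about 0.3 to 0.45 DAS28 units with 16% to 27% false positives on levels, or 0.13 to 0.19 units with 8% to 10% on change scores. With mild dependence the effect is small. The recording rates are assumptions with no source in the protocol, so these are not the trial's error rates, and the direction of any bias cannot be predicted. If controls were chosen because their records were complete, the same patients appear at every visit. The question then becomes selection of those who persisted and attended.

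This should be changed because a better analysis is cheap. If the control records prove complete, nothing is lost.

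**What to change.** In section 11, with matching wording in sections 4 and 7:

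1. Replace the separate visit tests for DAS28 and joint counts by one likelihood-based repeated-measures model with group, visit, group-by-visit and the week-0 value. Fit it to all available values from all eligible patients in both groups, whether or not their records are complete.
2. Set the same window around each visit in both groups, for example ±2 weeks, the widest that does not overlap at 4-week spacing.
3. Report the number measured per visit and group.
4. For week-24 remission (DAS28 ≤ 2.6, section 7), give bounds with all and then none of the unmeasured patients in remission, because the model does not remove bias from unrecorded current activity. With 20 of 30 controls measured, the control bounds would be 10/30 = 33 percentage points apart.
5. Treat any between-group ultrasound result as descriptive unless both groups have paired week-0 and week-24 scans.

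The cost is wording and modest extra analysis, available in SPSS, with no added patients, visits or procedures. The downside is that the between-group ultrasound comparison may be lost if few controls were scanned.
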